2.9 Activation of NK cells directly by TLR ligand

TLRs belong to the family of pattern-recognition receptors that trigger innate immune responses providing both immediate protection against various pathogens and instructing the adaptive immune system by the induction of dendritic cell recruitment and maturation.^{44,45} TLRs comprise 10 members so far identified in humans. Among these, TLR9 is highly expressed in plasmacytoid dendritic cells (pDCs) and B cells, and also expressed in NK cells.^{46,47,48,49} The molecular structure recognized by TLR9 consists of unmethylated deoxycytidyl-deoxyguanosine (CpG) dinucleotides in particular base contexts.⁵⁰ Synthetic oligodeoxynucleotides (ODNs) containing CpG motifs bind to TLR9 and activate pDC and B cells.⁵¹ TLR ligand can also directly activate NK cells. Hartmann et al. showed that ODNs containing specific CpG motifs up-regulated expression of the activation marker CD69 on NK cells and increased NK cell activity to lyse ⁵¹Cr-labeled K562 cells.⁵² An ODN with a TpC dinucleotides at the 5' end followed by three 6 mer CpG motifs (5'-GTCGTT-3') separated by TpT dinucleotides, that is ODN 2006 (CPG 7909), consistently showed the highest activity for human, chimpanzee, and rhesus monkey leukocytes. Sivori et al. demonstrated that in the presence of IL-12, freshly isolated NK cells responded to CPG 7909, and expressed CD69 and CD25 activation markers for all NK cell populations.⁵³ Further, NK cell stimulation also resulted in the induction of their functional activity as revealed by tumor necrosis factor- α and by up-regulation of cytolytic activity against tumor cells. As above, CpG ODNs, particularly CPG 7909, can directly activate NK cells through TLR9 signals.

2.10 Activation of NK cells by type I IFNs

Receptors of type I IFNs (IFNAR) are expressed in most tissues including NK cells.⁵⁴ In vitro experiment, type I IFNs enhance the ability of NK cells to kill target cells and to produce IFN- γ by indirect and direct mechanisms.^{55,56} In mouse model, Gidlund et al. demonstrated that NK-cell-mediated cytotoxicity against sensitive target cell lines was elevated in mice treated with IFNs, and that activation of NK-cell-mediated lysis under these conditions was blocked by the administration of antibodies neutralizing IFN- α / β .⁵⁷ Using IFN receptor, IFNAR1- and IFNAR2-deficient mice, as well as IFNAR1-blocking antibody, Swann et al. demonstrated that endogenous type I IFN is critical for controlling NK cell-mediated antitumor response in many experimental tumor models.⁵⁸ The type I IFNs are also crucial for DC-induced NK-cell activation and have an important role in the induction of NK-cell cytotoxicity in vitro and in vivo.^{59,60} TLR9-activated pDCs express high levels of costimulatory molecules, and secrete cytokines such as type I interferons, which then activate NK cells.

2.11 CpG infusion in vivo leads to secretion of type I IFNs

We recently showed that CpG infusion in vivo leads to secretion of type I IFNs in syngeneic transplantations model.⁶¹ In this model, donor mice were transferred with HA-expressing A20 B-cell lymphoma (A20-HA) on day -25 and naive clone 4 HA-specific T cells on day -15. On day -10, recipients were injected with A20-HA. On day 0, splenocytes and bone stem cells were harvested from tumor-bearing donor mice. Recipient mice were irradiated and then injected with a graft composed of Lin-c-Kit⁺ stem cells and A20 lymphoma-purged splenocytes. Fourteen days after transplantation, mice were vaccinated with either TNF- α -matured DC-HA or DC-Con with (CpG in vivo) or without (no CpG) administration of CpG in vivo. Some mice received DCs matured with CpG ex vivo followed by HA-pulsing (CpG ex vivo). Sera were harvested 12 hours after administration of CpG and measured for IFN- α by ELISA. As shown in Figure 1C, the high levels of serum IFN- α was detected in the CpG in vivo group, while no

significant INF- α production was detected in no CpG or CpG ex vivo group (Figure 1C). This result demonstrated that CpG infusion in vivo is critical for secretion of type I IFNs in mice.

Figure 1

[figure not shown]

Figure 7. A critical role for type I IFN in CpG-dependent reversal of tumor-specific T tolerance after transplantation. (A-C) Syngeneic transplants were set up as described in Figure 1A. Fourteen days after transplantation, mice were vaccinated with either TNF- α -matured DC-HA or DC-Con with (CpG in vivo) or without (no CpG) coadministration of CpG in vivo. Some mice received DCs matured with CpG ex vivo followed by HA pulsing (CpG ex vivo). Seven days after vaccination, the mean absolute number (\pm SD; $n = 4$) of CD4⁺CD25⁺Foxp3⁺ T cells per spleen in each group is indicated (A). CD4⁺CD25⁺ T_{Reg} cells (Suppressor) were isolated by FACS sorting and assayed for their suppressive capacity on naive CD4⁺CD25⁻ T cells (Responder) at the indicated ratios of suppressor to responder (S:R) using an in vitro suppression assay. Cultures were labeled with [³H]thymidine and harvested for scintillation counting. Results are expressed as mean CPM \pm SD (B). Sera were harvested 12 hours after administration of CpG and measured for IFN- α by ELISA (C). (D) Fourteen days after transplantation, mice were vaccinated with DC-HA or DC-Con coadministered with CpG in vivo. Six hours before and 24 hours after vaccination, mice were treated with neutralizing antibodies to mouse IFN- α and IFN- β (IFN- α β Ab) or a control Ab. Seven days after vaccination, splenocytes were stained with anti-CD8, anti-Thy1.1, and anti-IFN- γ antibodies, and the mean percentage (\pm SD; $n = 4$) of IFN- γ -secreting HA-specific T cells among total CD8⁺ T cells is indicated (D). Representative results of 2 independent experiments are shown.

(Horkheimer I, et al. Blood. 2009 May 21;113(21):5330-9.)

2.12 CpG activates NK cells directly, leading to lysis of lymphoma cells in vitro

To assess the direct effect of CpG on NK cell cytotoxicity against tumor cells, we co-cultured luciferase-expressing A20 B-cell lymphoma cells with purified NK cells alone (control) or NK cells in presence of CpG, IL-18, or CpG + IL-18. A20-luciferase viability was determined by measuring luciferase activity. Compared to control, NK cell cytotoxicity was substantially enhanced by adding CpG to the media (Figure 2). This preliminary result suggests that CpG directly increases NK cell cytotoxicity, leading to lysis of lymphoma cells in vitro.

[figure not shown]

Figure 2. CpG directly activates NK cytotoxicity on tumor cells. Purified NK cells were co-cultured with Luciferase expressing A20 lymphoma cells (A20-luc) in presence of CpG (10 μ g/ml), IL18 (20 ng/ml), or CpG + IL18. NK cells alone were used as a control. 3 days later, A20-luc viability was determined by imaging luciferase (A) and photons per second (p/s) were quantified and plotted (B).

2.13 CPG 7909 is safely used in multiple clinical studies (agent identical to the one we will make for this study, DUK-CPG-001)

CPG 7909 is a synthetic, nuclease-resistant, TLR9-activating ODN that mimics unmethylated CpG motifs. Antitumor activity has been suggested after treatment with CPG7909 as a single agent or as part of combination therapy in patients with several tumor types, including metastatic malignant melanoma,^{62,63,64} renal cell carcinoma,⁶⁵ non-small cell lung cancer,^{66,67,68,69} and non-Hodgkin lymphoma.^{70,71,72,73} Leonard et al. conducted Phase I trial of CPG 7909 with and following Rituximab in 50 patients with recurrent indolent and aggressive non-Hodgkin lymphoma.⁷⁴ Patients received Rituximab and CPG 7909 weekly for 4 weeks either intravenously (0.04, 0.16, 0.32, or 0.48 mg/kg) or subcutaneously (0.01, 0.04, 0.08, or 0.16 mg/kg). An additional extended-treatment cohort received 4 weeks of 0.24 mg/kg subcutaneously in combination with Rituximab followed by CPG 7909 alone subcutaneously weekly for 20 weeks. Most common adverse events were mild to moderate systemic flu-like symptoms and injection-site reactions. Objective responses occurred in 12 of 50 patients overall and in 6 of 12 patients in the extended treatment cohort, including 2 patients with Rituximab-refractory disease. Pashenkov et al.⁷⁵ conducted Phase II trial with a CPG7909 in 26 melanoma patients. CPG7909 was administered at a total dose of 6 mg subcutaneously once weekly in an outpatient setting for 24 weeks or until the development of progressive diseases. Laboratory and non-laboratory adverse events were limited, transient, and did not result in any withdrawals. Two patients experienced a confirmed partial response, and three patients experienced stable disease. Immunologic measurements revealed induction of an activated phenotype of pDC, elevation of a surrogate marker of serum type I IFN production, and significant stimulation of NK cell cytotoxicity, which was associated with clinical benefits. NK cytotoxicity showed divergent dynamics: an up to 30.1-fold increase was measured in 3 of 4 patients with partial response and stable disease and a decrease was observed in seven of the nine patients with progressive disease. This finding supported the findings in in vitro/in vivo study that CPG 7909 can activate NK cells directly through TLR9 or indirectly through type I IFNs signals.

From these findings, our identical agent DUK-CPG-001 with NK cell-enriched DLI could be a potentially effective strategy to enhance immune recovery and anti-tumor activity through NK cell activation and obtain better clinical outcomes.

2.14 Summary:

Graft-versus-tumor effects are critical in allogeneic stem cell transplantation, and can be enhanced by DLIs. However, the use of non-selected DLIs is limited by the risk of acute GVHD. We have shown that 1-step, high-yield process of NK cells is feasible, and results in high doses of NK cells infused with little toxicity. NK cell-enriched DLIs resulted in improved immune recovery and outcomes for some patients. Infusion of TLR9 agonist, CPG 7909, in mice leads to secretion of type I IFNs, which can activate NK cells. TLR ligand also directly activates NK cells. Our preliminary data showed that CPG 7909 directly activated NK cell function, leading to lysis of lymphoma cells. CPG 7909 has been already used in many studies, and shown to be safe. NK cells activation was also observed in clinical trials. In this study, we will evaluate the rates of progression-free survival and unacceptable toxicity in patients receiving NK cell-enriched DLIs when administered alone or administered with the TLR9 agonist, DUK-CPG-001, from a 8/8 HLA-matched related or unrelated donor (Cohort A) or 4-7/8 HLA-matched related donor (Cohort B) following allogeneic stem cell transplantation.

3 ELIGIBILITY CRITERIA

3.1 Inclusion criteria

1. Patients with hematologic diseases who have undergone an allogeneic transplantation, using a 7-8/8 HLA-matched related or unrelated donor or 4-6/8 HLA-matched related donor. This may include patients with a mixed chimeric state or disease persistence or at high risk of relapse (these are patients who do not fit exclusionary principle 3 below).
2. Performance status must be ECOG PS 0, 1, or 2.
3. Donor cellular engraftment of at least 2.5%.
4. < Grade 2 acute GVHD at time of the first NK cell-enriched DLI. Patients with treated acute GVHD must be on a stable dose of therapy (no increase in immunosuppressive therapy for the 2 weeks before planned NK cell-enriched DLIs). The dosage/level of immunosuppressive therapy at the time of NK-DLIs should be no greater than 20mg of prednisone daily or mycophenolate 500 mg bid daily or cyclosporine with a target level of 200 ng/mL or tacrolimus with a target level of 10 ng/ml.
5. Estimated survival of at least 8 weeks.
6. Age of \geq 18 years.
7. Females of childbearing potential should have a negative serum beta-HCG test within 48 hours of beginning DLI and/or DUK-CPG-01 unless contraception is used after initial testing. *A female of childbearing potential (FCBP) is a sexually mature female who: 1) has not undergone a hysterectomy or bilateral oophorectomy; or 2) has not been naturally postmenopausal for at least 24 consecutive months (i.e., has had menses at any time in the preceding 24 consecutive months).*

8. Males must agree to use a medically acceptable form of birth control in order to be in this study and for 3 months after infusion

3.2 Exclusion criteria

1. Pregnant or lactating women.
2. Patients with other major medical or psychiatric illnesses, which the treating physician feels, could seriously compromise tolerance to this protocol.
3. Patients likely to have a significantly better durable response to allogeneic transplant alone (better than 60% progression free longer than 2 years) includes: those with myeloproliferative diseases or hemoglobinopathies with over 50% T cell subset engraftment (assessed around 100 days post transplant); It is not anticipated that any such patients would be transplanted within our program, however but those in first remission AML patients with good risk standard genetics or normal genetics with either NPM1 or CEBPA mutations, first chronic phase CML without kinase gene mutations, follicular lymphoma patients in first remission who only required 1 regimen to attain remission all would be excluded from this protocol.

3.3 HLA 4-8/8 matched related donor inclusion/exclusion criteria (criterion below are recommended but may evolve to follow current program standards) to be completed within 30 days of apheresis per standard guidelines

1. Adult donors must be an HLA 4-8/8 match with the patient
2. Potential donors under the age of 18 must have a single patient exemption approved by the IRB.
3. Donor must not have any medical condition which would make apheresis more than a minimal risk, and should have the following:
 - (a) Family members will be considered for donation if they do not have a history of known cardiac problem and do not have abnormal cardiac findings by physical examination. Those with a history of cardiac problems or abnormal cardiac findings by physical examination should undergo a stress evaluation or be evaluated by a cardiologist and deemed eligible to donate.
 - (b) Documented bilirubin and hepatic transaminases of $\leq 2.5 \times$ ULN,
 - (c) Documented adequate hematologic parameters including a hematocrit $> 35\%$ for males and 33% for females, white blood cell count of $\geq 3,000$, and platelets $\geq 80,000$.
 - (d) FACT labs and final test results available prior to infusion into the patient (copy of labs included in appendices). In the second donation from the donor, the FACT labs must be redrawn within 30 days of initiation of apheresis. Positive serologies are not repeated as they remain positive for lifetime.
4. Females of childbearing potential should have a negative serum beta-HCG test within 48 hours of beginning apheresis unless contraception is used after initial testing. *A female of childbearing potential (FCBP) is a sexually mature female who: 1) has not undergone a hysterectomy or bilateral oophorectomy; or 2) has not been naturally postmenopausal for at least 24 consecutive months (i.e., has had menses at any time in the preceding 24 consecutive months).*

- 3.4 8/8 HLA matched unrelated donors** will be matched at least as HLA -A, -B, C and -DRB1. Criterion for donation will be those allowing donation following the NMDP accepted donor criterion and program SOPs for the typical matched unrelated donors.

4. TREATMENT PLAN

4.1 Patient prior to starting therapy

Within 21 days prior to the 1st NK DLI, patients will be screened as follow:

- An updated medical history will be collected
- A physical examination performed including a pregnancy test, if the patient is a female of childbearing potential.
- Labs:
 - CBC (with differential preferred),
 - creatinine,
 - AST, ALT, and total bilirubin,
 - calcium,
 - LDH,
 - potassium,
 - sodium,
 - bicarbonate,
 - chloride and glucose,
 - albumin,
 - phosphorous,
 - magnesium and
 - alkaline phosphatase
 - Immune reconstitution panel
- Patients will have blood or marrow stored for chimerism analysis.
- Research blood samples for analysis of immune function.
- Stool will be collected for analysis of microbiota
- Tests documenting the patient's disease state:
- Bone marrow aspirate and biopsy for patients with known abnormalities of the marrow previous to the transplant should have tests repeated to check for the prior abnormalities such as morphology, flow cytometry, PCR, or cytogenetics.
 - Blood studies, and/or
 - Radiographic tests such as CTs, MRI, PET scans as determined by treating physician, for standardized response evaluations as outlined in section 4.3.2).

4.2 Donor apheresis and cell processing

Donors will return to the center for a fresh collection of NK cells and they will not need growth factor mobilization. One collection will be used for each NK cell infusion. Cells will be transfused immediately after collection and processing or the next day. Cell processing will be performed in our cryopreservation lab according to SOP for collection, labeling and handling. The cells will be NK selected using a CD56 antibody (CliniMACS CD56 Reagent), ClinIMACS^{plus} instrument and ClinIMACS tubing set provided by Miltenyi Biotec using the company protocol (Miltenyi Biotec Inc, Auburn, California). Pre and post processing cell count, viability, Hematopoietic Progenitor Cell Assay (HPCA) and flow analysis per SOP will be done.

* Viability must be confirmed as $\geq 70\%$ to release the product for infusion. Product with $< 70\%$ viability will not be infused into the patient. Repeat collection may be attempted at the treating physician's discretion. Similarly, CD56+ cell yield and purity will be available prior to infusion of cell product to make sure that the acceptance criteria are met. The acceptance criteria are $\geq 70\%$ for purity and $\geq 40\%$ for yield. The expected purity % and yield % is 96 \pm 8 and 83 \pm 21 in 6/6 HLA-matched related donor, respectively, and 97 \pm 3 and 77 \pm 24 in 3-5/6 HLA-

matched related donor, respectively.⁷⁶ Failure to meet the acceptance criteria for yield and purity will represent device performance failure which will be recorded, investigated and reported to the FDA.

4.3 Patient Evaluation

- 4.3.1 Patients must remain in clinic for at least 2 hours post-infusion for observation.
 - Vital signs must be checked every 30 minutes

- 4.3.2 Assessment of disease will use standardized criteria and shall include a careful examination of the studies needed to detect the disease (for example, PET, radiographs, immuno-phenotype, marrow, molecular studies etc.).^{77, 78, 79, 80, 81, 82} Restaging may be altered at the discretion of the transplant physician following the patient (who are all subinvestigators in this study) if the patient is felt to be progressing before these time points but the recommended restaging is 3,6, and 12 months for 1 year after the last NK-enriched DLI, q6 months for the next 2 years, then as indicated clinically.
 - ❖ Assessment of disease is required prior to each NK cell-enriched DLI, and 3,6, and 12 months for 1 year after the last NK-enriched DLI, then q6 month for the next 2 years.
 - ❖ Immune reconstitution studies prior to and 1 day and 1 month after each NK cell-enriched DLI, and 3, 6, and 12 months after the last NK-enriched DLI.
 - ❖ Determination of chimerism (by short tandem repeat analysis in use in our DUKE HLA laboratory with a 2% sensitivity) just prior to each NK cell-enriched DLI, and 3, 6, 12 months after the last NK-enriched DLI.

- 4.3.3 Toxicity will be formally evaluated by the protocol investigators, health care professionals directly under the supervision of protocol investigators, or physicians specifically trained in hematopoietic cell transplant will monitor the subjects' safety at appropriate intervals up until at least two years after NK infusion. Monitoring will occur 1 day post infusion and 1 month later (more as determined by treatment team) and, then 3, 6, and 12 months post-second DLI for the first year post-second DLI.

Assessments performed include the following for toxicity assessment following the NCI common toxicity criteria (version 4) and standard GVHD criteria (appendix I).:
 - Medical history (specific to GI toxicity as well as overall new problems),
 - Physical exam,
 - CBC,
 - Liver function tests (AST, ALT, bilirubin at a minimum), and
 - Chemistry CS to include creatinine and BUN

The tests and procedures are not in addition or in excess of our standards for allogeneic transplants outside of this protocol. The transplant team is available for constant communication with the patients and their local physicians to monitor their toxicities. Further follow up at the transplant center will be required as needed if the patient has a toxicity due the transplant or infusion procedures. Patients with a grade 3 or greater toxicity

due to the study will be seen every other week at a minimum until the toxicity is < grade 3, and then will be seen as clinically appropriate.

NOTE: If a patient does not receive the 2nd DLI, they will be followed every 3 months after their 1st DLI.

4.3.4 Stool Collection and Microbiome Analysis:

We will collect stool samples from patients at the following time points throughout the study: pre-DLI, 1 month post, pre-second DLI, 1 month post, then at 3, 6 and 12 months after last DLI for one year. Stool samples from patients may be stored at 4°C for up to 24 h before freezing at -80°C for batch analysis. Samples not used during this research will be stored in the Duke Data and Specimen Repository (IRB Pro00006268) unless the patient does not consent to the Repository. If no consent to store the samples is obtained, the samples will be destroyed after study analyses are complete.

To analyze the gut microbiome, DNA will be extracted from fecal samples⁹¹ and gut flora bacterial density will be quantified using real-time quantitative polymerase chain reaction (qPCR) as described.⁹² We will amplify 16S ribosomal RNA (rRNA) using Illumina HiSeq platform and analyze the data using the Qiime script package with parallel processing.⁹³ Sequences will be de-noised and clustered at 97% identity using USEARCH and aligned to the 16S rRNA gene, using the align.seqs.py wrapper with the PyNAST algorithm and Greengenes reference alignment. Based on these results, we will calculate diversity (Shannon Diversity, primary endpoint, and Chao1) and construct phylogenetic trees using computational analysis software.

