4.4 Patient NK cell infusion and CpG administration plan

This treatment regimen may be administered on an outpatient basis.

4.4.1 NK cell-enriched DLI:

The target cell dose for NK cell-enriched DLI will be as many cells as can be collected with less than 0.5×10^6 CD3+ CD56- cells/kg patient weight in the 4-6/8 HLA-matched related setting and 1×10^6 CD3+ CD56- cells/kg patient weight in the 7-8/8 HLA-matched related or unrelated setting. The first NK cell-enriched DLI will be administered between one to six months post-transplant. The second NK cell-enriched DLI will be administered one to three months post the first infusion, in patients who have < grade II aGVHD at the time of infusion and have not had unacceptable toxicities (see 6.2.1 Definition of unacceptable toxicity) that are at least possibly related to the previous DLI and resolved to grade 1 or less. The second DLI will NOT be administered in patient with \geq grade III aGVHD at the time of infusion or unacceptable toxicities at least possibly related to the first infusion. If patients have GVHD and were on immunosuppressive therapy at study entry, patients will continue on their stable dose of immunosuppressive agents started for therapy of acute GVHD before the NK cell-enriched DLI, and will not taper until at least 6 weeks following the each NK cell-enriched DLI (unless disease progression or patient toxicity from the agents requires earlier taper). The donor NK cells will be infused over 30 minutes. Diphenhydramine 25 mg iv or po, and Acetaminophen 650 mg po will be used prior to each reinfusion, unless there is a history of allergy or contraindication in the patient, in which case hydrocortisone 50mg IV will be used.

These cells are infused into the patient via a peripheral intravenous line or central line. If signs of GVHD occur after NK cell-enriched DLI, immunosuppressive agents (prednisone, cyclosporine, tacrolimus and/ or mycophenolate preferred first choices) may be started.

4.42 Adverse effect of NK cell-enriched DLI:

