6.1.1 Definition of progression-free survival

Progression-free survival is defined from the day of the first NK cell-enriched DLI until the day of disease relapse, disease progression, or death whichever comes first. Patient without relapse, progression, or death will be censored at the last follow-up.

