6.1.2 Statistical considerations

Cohort A (7-8/8 HLA-matched related or unrelated transplantation)

A 2-stage MiniMax design⁸⁶ will be used to test the null hypothesis that the progression-free survival rate is \leq 46% against the alternative hypothesis that it is \geq 71% in each arm. Nine patients will be treated in the first stage. If the number of patients who are alive without relapse/progression is equal to 4 or less at 1 year after transplantation in one arm, then the study for the arm will be terminated and the treatment is ineffective. If there are at least 5 patients (56%) who are alive without relapse/progression at 1 year after transplantation, the sample size will be increased up to a maximum of 25 patients. If the number of patients who are alive without relapse/progression is

equal to 15 or less at 1 year after transplantation, then the treatment is ineffective. If there are at least 16 patients (64%) who are alive without relapse/progression at 1 year after transplantation, this protocol will be deemed effective. This design has a significance level of 0.05, a power of 0.80, a probability of early termination under the null of 0.60, and an expected sample size under the null of 16 patients.

Table 4

Stage	Total Accrual	Close study/therapy if number of patients who are alive without relapse/progression is \leq
1	9	4 (44%)
2	25	15 (60%)

Cohort B (4-6/8 HLA-matched related transplantation)

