Appendix IV: Donor Eligibility Checklist

Desired answer	Answer	Date determined	Eligibility Criteria
4-8/8 HLA matched related donor			
yes			Potential donors under the age of 18 must have a single patient exemption approved by the IRB.
yes			Family members will be considered for donation if they do not have a history of known cardiac problem and do not have abnormal cardiac findings by physical examination. Those with a history of cardiac problems or abnormal cardiac findings by physical examination should undergo a stress evaluation or be evaluated by a cardiologist and deemed eligible to donate.
yes			Documented Bilirubin and hepatic transaminases < 2.5 x ULN
yes			Documented Adequate hematologic parameters including a hematocrit > 35% for males and 33% for females, white blood cell count of $\geq 3,000$, and platelets $\geq 80,000$.
yes			FACT labs and final test results available prior to infusion into the patient (copy of labs included in appendices). In the second donation from the donor, the FACT labs must be redrawn within 30 days of initiation of apheresis. Positive serologies are not repeated.
yes			Females of childbearing potential should have a negative serum beta-HCG test within 1 week of beginning apheresis.
8/8 HLA matched unrelated donor			
yes			Donor is an NMDP matched unrelated donor (Note: If yes, checking the above eligibility criteria is not needed).

Appendix V: Schedule of Events (This chart is a guide and full protocol takes precedence over this chart)

Table 9

NK cell-enriched DLI	1 st DLI ⁴			2 nd DLI ⁵ (if performed)			After the last DLI ⁹			
	Pre ¹	Post 1day	Post 1M ¹⁰	Pre ¹	Post 1day	Post 1M ¹⁰	Post 3M ¹¹	Post 6M ¹¹	Post 12M ¹ ¹	Q6 mos x 4 ¹¹
History and Physical	x		x		x		x	x		x
Blood tests for routine monitoring ²	x		x		x		x	x		x
Serum Pregnancy testing ⁸	x			x						
Assessment of disease ³	x			x ⁷			x	x		x
RFLP (blood or marrow)	x			x ⁶			x	x		x
Chimerism	x			x			x	x		x
Immune Reconstitution	x	x	x	x	x	x	x	x		x
Research blood Samples	x	x	x	x	x	x	x	x		x
Stool collection	x		x	x		x	x	x		x

¹ Screening, within 1-3 weeks prior to DLI

² Pre-infusion: CBC (with differential preferred), creatinine, AST, ALT, and total bilirubin, calcium, LDH, potassium, sodium, bicarbonate, chloride and glucose, albumin, phosphorous, magnesium and alkaline phosphatase. Post-infusion: CBC (with differential preferred), creatinine, AST, ALT, total bilirubin, and BUN

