³ Restaging will use standardized criteria and shall include a careful exam of the studies needed to detect the disease (PET, radiographs, immunos, marrow, molecular studies etc.). Restaging may be altered at the discretion of the transplant physician following the patient (who are all sub-investigators in this study) if the patient is felt to be progressing before these time points but the recommended restaging is q3 months for 1 year after the last NK-enriched DLI, q6 months for the next 2 years.

⁴ The first NK cell-enriched DLI will be administered at 1-6 months post-transplant.

⁵ The second NK cell-enriched DLI will be administered 1-3 months post the first infusion, in patients who have < grade II aGVHD at the time of infusion and have not had unacceptable toxicities (see 6.2.1 Definition of unacceptable toxicity) that are at least possibly related to the previous DLI and resolved to grade 1 or less. The second DLI will NOT be administered in patient with \geq grade III aGVHD at the time of infusion or unacceptable toxicities at least possibly related to the first infusion.

⁶ Marrow does not need to be redrawn if the patient is in a complete remission based on marrow collected within 30 days of DLI.

⁷ Scans do not need to be performed if the patient is in a complete remission based on scans performed within 30 days of DLI.

⁸ For females of childbearing potential only.

⁹ If the 2nd DLI is unable to be performed, follow-up will be from the time of 1st DLI.

¹⁰ A window of +/- 2 days is allowed.

¹¹ A window of +/- 2 weeks is allowed.

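### Restaging is timed from the last DLI, so no required disease assessment is tied to the 1-year point that decides primary objectives 1 and 2

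*Combined protocol and SAP*

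**What the plan says.** Three anchors are in use.

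- **Restaging (4.3.2):** "Assessment of disease is required prior to each NK cell-enriched DLI, and 3,6, and 12 months for 1 year after the last NK-enriched DLI". The anchor is the last DLI.
- **Endpoint definition (6.1.1):** "Progression-free survival is defined from the day of the first NK cell-enriched DLI". The anchor is the first DLI. Patients without an event are censored at last follow-up.
- **Decision rules (6.1.2, both cohorts):** the count is of patients "alive without relapse/progression at 1 year after transplantation". The anchor is transplantation.

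The anchors differ by months. Section 4.4.1 places the first DLI 1 to 6 months after transplantation, and "The second NK cell-enriched DLI will be administered one to three months post the first infusion". For patients who get only one DLI, the note in 4.3.3 (the toxicity section) says: "If a patient does not receive the 2nd DLI, they will be followed every 3 months after their 1st DLI".

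Appendix V, footnote 3, gives a different restaging frequency: "the recommended restaging is q3 months for 1 year after the last NK-enriched DLI". The appendix also says "This chart is a guide and full protocol takes precedence over this chart", so the 3, 6 and 12 month schedule of 4.3.2 governs. Footnote 11 applies to the visits after the last DLI: "A window of +/- 2 weeks is allowed".

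No passage says how to classify a patient who was not assessed at 1 year, or how to date a progression found at a later visit.

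**The concern.** Each arm's verdict rests on a count of at most 25 patients with known status at 1 year. One patient separates failure from success: 15 against 16 in Cohort A, 12 against 13 in Cohort B. If no restaging falls at the 1-year point, a relapse that is not clinically evident may be found only at the next visit. Whether that patient counts as a success or a failure then depends on a convention the plan does not state.

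On the first-DLI clock the gap also depends on how many DLIs a patient received. Under 4.4.1 that number depends on GVHD and toxicity after the first infusion, so how closely disease is watched near the endpoint depends on an outcome of treatment.

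**Working it through.** **1. The plan's own designs.** Inputs from 6.1.2: Cohort A has r1/n1 = 4/9, r/n = 15/25, p0 = 0.46, p1 = 0.71. Cohort B has 4/12, 12/25, p0 = 0.34, p1 = 0.59. The exact probability of declaring an arm effective is the sum over k > r1 of P(X1 = k) × P(X2 > r − k), where X1 and X2 are binomial with sizes n1 and n − n1.

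| | Type I error | Power | Early termination under null | Expected N under null |
|---|---|---|---|---|
| A | 0.0485 | 0.803 | 0.598 | 15.4 |
| B | 0.0456 | 0.802 | 0.612 | 17.0 |

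The stated figures are reproduced (0.05 is the ceiling).

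**2. Visits on the first-DLI clock.** With the second DLI at month d, visits fall at d + 3, d + 6 and d + 12. For d = 1 to 3 these are months 4-6, 7-9 and 13-15. The 2-week window brings the last visit no earlier than 13 − 0.5 = month 12.5. A one-DLI patient is assessed at month 12. If footnote 3 were followed, its extra visit at d + 9 (months 10-12) would lie within 2 weeks of month 12 only for d of about 2.5 to 3.

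**3. Visits on the transplant clock.** Assume timings are spread evenly over the allowed ranges: first DLI at 1-6 months, second 1-3 months later. Let L be the month of the last DLI.

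- *Two DLIs, 3/6/12 schedule.* A visit lies within 2 weeks of month 12 if L is 5.5-6.5 (6-month visit) or 8.5-9 (3-month visit). The density of L is 2/(5 × 2) = 0.2 in the first interval, which contributes 1 × 0.2 = 0.20. The second contributes (0.5²/2)/10 = 0.0125. The total is about 21%.
- *One DLI.* The DLI must fall at months 5.5-6, which gives 0.5/5 = 10%. Three-monthly visits add DLI times of 2.5-3.5 months, another 1/5, for 30%.

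**4. If unassessed patients are counted as progression-free.** Assumptions, none from the documents except as noted:

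- Constant hazard at the null rate, so S(t) = p0^(t/12).
- Second DLI at month 2, so the last visit before the landmark is month 8.
- A share s = 0.25 to 0.50 of events between months 8 and 12 is still unknown at month 12.
- A share f = 0.37 to 1 of patients gets two DLIs. The lower end comes from the pilot in 2.8: 51 infusions in 30 patients with at most 3 each leaves 21 repeat infusions, so between 11 and 21 of 30 patients (37-70%) had at least two.

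Apparent 1-year PFS = p0 + f × s × (p0^(8/12) − p0). The gap is 0.596 − 0.46 = 0.136 in A and 0.487 − 0.34 = 0.147 in B.

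| f | s | A: apparent PFS | A: type I error | B: apparent PFS | B: type I error |
|---|---|---|---|---|---|
| 0.37 | 0.25 | 0.472 | 0.062 | 0.353 | 0.061 |
| 0.37 | 0.50 | 0.485 | 0.079 | 0.367 | 0.081 |
| 0.70 | 0.50 | 0.508 | 0.117 | 0.391 | 0.127 |
| 1 | 0.50 | 0.528 | 0.162 | 0.414 | 0.180 |

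**5. If status is read from the next visit.** At month x = 13 to 15 the rate becomes p^(x/12). With every patient given two DLIs:

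| x | A: type I error | A: power | B: type I error | B: power |
|---|---|---|---|---|
| 13 | 0.026 | 0.739 | 0.022 | 0.724 |
| 14 | 0.013 | 0.670 | 0.010 | 0.638 |
| 15 | 0.006 | 0.597 | 0.005 | 0.549 |

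If only 37% of patients get two DLIs, the success rate under the alternative is 0.37 × p1^(x/12) + 0.63 × p1, and power is 0.734-0.780 (A) and 0.720-0.775 (B).

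**The case against.** **Patients with two DLIs do not always miss the decision date.** A reader might infer that they have no assessment at the point that decides the objectives, whichever clock is used. The documents do not support this. The rules in 6.1.2 count from transplantation, and 4.4.1 allows DLIs at months 4 and 6, which puts the 6-month visit at month 12. On that clock the gap is also not confined to patients with two DLIs. This narrows the statement about who is affected, but most timings of either kind still miss.

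**Upward bias is not established.** Deaths are captured when they occur, and 4.3.2 allows earlier restaging when progression is suspected, so only relapse that is not clinically evident is exposed. Reading the next visit reverses the direction. Section 2.3 does not give the assessment schedule behind the historical 46% and 34%, so the net bias against the null cannot be determined. All of this stands.

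**The largest figures are worst cases within the illustration.** Type I error of 0.16 and 0.18 needs every patient to receive two DLIs and half of the gap events to be missed. With three-monthly restaging (last visit at month 11), the same two assumptions give only 0.066 (A) and 0.065 (B). This also stands, which is why ranges are given.

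**Comparability of the arms is not a primary issue.** Each arm is tested against a fixed null, and no between-arm PFS test is planned.

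**An edge case exists.** The shift of up to 4 weeks in 4.6.1 could bring the second DLI close to the first and so place the 12-month visit near month 12. It does not remove the general gap.

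**Conclusion.** The concern holds in a limited form. Restaging follows the last DLI, while the endpoint follows the first DLI or transplantation, so no required assessment is tied to the 1-year landmark. On the first-DLI clock, a patient given two DLIs at the interval in 4.4.1 has no required assessment at month 12, even with the 2-week window. On the transplant clock, only about 20% of two-DLI timings and 10% of one-DLI timings have a visit there, assuming an even spread.

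The direction of the error is open. It is upward if unassessed patients are carried forward as progression-free, and downward if status is read at months 13-15. On the assumptions above, type I error would be about 0.06-0.16 (A) and 0.06-0.18 (B) in the first case. In the second, power would be 0.60-0.74 (A) and 0.55-0.72 (B) if all patients receive two DLIs, and closer to 0.80 if fewer do. These are scenarios, not estimates. The first-DLI visit times and the lack of a classification rule follow from the text alone. The point is a should-fix.

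**What to change.** 1. Reconcile 6.1.1 and 6.1.2 to one PFS origin. This comes first: visits moved to the first DLI would still miss a landmark counted from transplantation.
2. In 4.3.2 and Appendix V, time the disease assessments from that origin for every patient, whatever the number of DLIs. Include one at 12 months within 2 weeks, and read 1-year status from it. Keep the assessment before the second DLI. If transplantation is chosen, the 3- and 6-month visits may precede the first DLI, so the 12-month visit is the essential one.
3. State that progression is dated at the assessment that detects it. Count a patient with no assessment in the window as not progression-free, unless a later assessment shows no progression.
4. Reconcile 4.3.2 (3, 6 and 12 months) with Appendix V footnote 3 (every 3 months).
5. Leave toxicity and immune follow-up as they are, including the 4.3.3 note for one-DLI patients.

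The cost is an amendment. The designs and the 25 patients per arm do not change, and the number of required restagings need not rise: with the first DLI as origin, existing visits move 1 to 3 months earlier in two-DLI patients. The downside is that some restaging visits will no longer coincide with the immune, chimerism and toxicity visits timed from the last DLI, so some patients will attend more often.
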